7.5.2 Resumption of a Halted Study

The IND Sponsor, in collaboration with the PI and DSMB will determine if it is safe to resume the study. The CSO or designee will notify the Site Investigators of the decision on resumption of the study. The Site Investigators will notify their local IRB(s) of the decision.

7.5.3 Discontinuation of Study Agent/Intervention

Subjects who do not resume study agent/study intervention will continue to be followed for safety per protocol or as clinically indicated, whichever is more conservative.

7.6 Safety Oversight

7.6.1 Safety Review and Communications Plan (SRCP)

A Safety Review and Communication Plans (SRCP) has been developed for the protocol. The SRCP is an internal communications document between the PI and the IND Sponsor CSO, which delineates the safety oversight responsibilities of the PI, the CSO, and other stakeholders. The SRCP also includes the overall plan for conducting periodic safety surveillance assessments.

The IND Sponsor and the PI will sign a formal Transfer of Regulatory Obligations (TORO)/SRCP which documents that the PI has accepted the responsibility for periodic safety surveillance assessments as outlined in 21 CFR 312.32(b).

7.6.2 Sponsor Medical Monitor

A Medical Monitor representing the IND Sponsor (OCRPRO), will be appointed for oversight of safety in this clinical study. The Sponsor Medical Monitor will be responsible for performing safety assessments as outlined in a Safety Review and Communications Plan (SRCP) as defined in Section [7.6.1](#).

7.6.3 NIAID Intramural Data and Safety Monitoring Board

The NIAID Intramural DSMB includes independent experts that do not have direct involvement in the conduct of the study and have no significant conflicts of interests as defined by NIAID policy. The NIAID Intramural DSMB is constituted to review the safety data of Intramural NIAID clinical studies that require DSMB oversight, and consists of experts in infectious diseases, biostatistics, and clinical trials. The PI/designee will provide the DSMB Executive Secretary with blinding codes in a sealed envelope in case the DSMB requires this information to make its recommendations. The DSMB will review the study prior to initiation and twice a year thereafter. The Board may convene additional reviews as necessary. Prior to each review, the PI will submit a summary of cumulative safety data in a format acceptable (by unblinded cohort if requested) to the Board. The Board will review the study data to evaluate the safety, efficacy, study progress and conduct of the study. Reports of SAEs and deaths will be submitted by the PI to the Board at the same time they are reported to the Sponsor and IRB. All Unanticipated Problems will be submitted to the DSMB at the same time they are submitted to the IRB or IND Sponsor. IND Safety Reports will be submitted to the DSMB by the investigator after their receipt. The PI will notify the DSMB of any cases of intentional or unintentional unblinding as soon as possible. The PI will notify the Board at the time halting are met and obtain a recommendation concerning continuation, modification, or termination of the study. The PI will submit the written DSMB summary reports with recommendations to the IRB(s).

The DSMB will receive summary data in an unblinded manner to determine whether or not dose expansion or dose escalation will occur. The DSMB will be responsible for:

1. Determining if the criteria for a suitable CHIM strain has been met. These criteria are:
 - a) $\geq 80\%$ of inoculated subjects develop detectable viremia by virus culture *and*
 - b) The mean peak titer of ZIKV recovered is $2 - 3 \log_{10}$ PFU/mL.
 - c) The committee will review the clinical signs and symptoms induced by the ZIKV strain, but signs and symptoms will not be required for dose escalation.
2. Recommending whether or not dose-escalation should occur. Dose escalation may occur even if the above criteria for a suitable CHIM strain have been met if it is believed that more consistent outcomes would be achieved with a higher dose, or if evaluating the shedding of virus given at a higher dose would improve the scientific understanding of ZIKV infectivity, shedding, and possibly transmission.

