2. Seven subjects from cohort 3 and 7 subjects from cohort 4 will be selected for mosquito-feeding. They will also be randomized 5:2 (ZIKV:placebo) to ensure the clinical team remains blinded to the treatment assignment.

Product Description: ZIKV-SJRP/2016-184 and ZIKV-Nicaragua/2016 were isolated directly from the serum of subjects who were diagnosed with uncomplicated Zika illness. Each virus will first be evaluated at a dose of 10² plaque-forming units (PFU). At each subcutaneous dose, the virus will first be evaluated in 7 subjects (5 will have received ZIKV, 2 will have received placebo). The remaining subjects in each dose cohort will be inoculated with the current dose or dose escalation will occur according to predetermined criteria.

Primary Study Objective: Identify a suitable strain of ZIKV for use in safety-assured CHIM studies by:

1. Determining the proportion of infected subjects who demonstrate clinical signs/symptoms of Zika infection (fever, rash, conjunctivitis, pruritis, myalgia, arthralgia, headache) by ZIKV strain and dose
2. Determining the quantity and duration of ZIKV in blood, urine, cervico-vaginal secretions, semen, and saliva by culture (infectious virus) and by reverse transcriptase – polymerase chain reaction (RT-PCR)
3. Determining if dose correlates with incidence/duration of ZIKV in blood, urine, cervico-vaginal secretions, semen, and saliva

A suitable ZIKV strain for CHIM studies is defined as one in which:

1. $\geq 80\%$ of ZIKV or DENV-naïve inoculated subjects develop detectable viremia, as determined by direct virus culture **and**
2. Infectious virus is detected on more than 1 day for $\geq 80\%$ of subjects with detectable viremia **and**
3. The geometric mean peak titer of virus recovered by culture is $2.0 - 3.0 \log_{10}$ PFU/mL

Ideally, the ZIKV strain would also induce one or more of the following clinical signs in $\geq 50\%$ of infected subjects, however this will not be included in dose escalation criteria.

- a) Fever
- b) Rash
- c) Non-purulent conjunctivitis
- d) Myalgia
- e) Arthralgia

Secondary Study Objectives:

1. Characterize the clinical presentation of acute ZIKV infection by assessing the frequency of adverse events (AEs), graded by severity, occurring within 28 days of ZIKV administration
2. Longitudinal analysis of virus present in blood, urine, saliva, cervico-vaginal secretions, and semen
3. Time course of the neutralizing antibody response to ZIKV infection

Exploratory Objectives:

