2 OBJECTIVES

2.1 Primary Objectives

- Determine the suitability of both ZIKV strains for use in a safety-assured Zika CHIM. Suitability will be assessed by:
 - The frequency and severity of clinical signs and symptoms of infection such as fever, rash, conjunctivitis, myalgia, arthralgia, and headache following ZIKV administration compared with placebo.
 - The infection frequency of ZIKV by strain and by dose. Infection is defined as recovery of ZIKV (determined by RT-PCR or culture) from blood, urine, cervico-vaginal secretions, semen, or saliva and/or by seroconversion to ZIKV (50% plaque reduction neutralization titer [PRNT₅₀] ≥ 1:10) by 90 days post-administration of the ZIKV strain.

- The frequency, magnitude, and duration of ZIKV presence in the blood, urine, cervico-vaginal secretions, semen, and saliva by both RT-PCR and virus titration in tissue culture by ZIKV strain and dose.
- A suitable ZIKV CHIM strain is defined as one that:
 - a. $\geq 80\%$ of ZIKV and DENV-naïve inoculated subjects develop detectable viremia by virus culture (infectious virus) **and**
 - b. Infectious virus is detected on more than 1 day for $\geq 80\%$ of subjects with detectable viremia **and**
 - c. The mean peak titer of infectious virus recovered from subjects is $2 - 3.0 \log_{10}$ PFU/mL

Ideally $\geq 50\%$ of ZIKV and DENV-naïve inoculated subjects will develop ≥ 1 of the following clinical signs thought to be definitely, probably, or possibly due to the ZIKV strain, however this will not be required for dose expansion or dose escalation:

 - i. Fever
 - ii. Rash
 - iii. Non-purulent conjunctivitis
 - iv. Myalgia
 - v. Arthralgia

A mean peak titer of $2.0 - 3.0 \log_{10}$ PFU/mL should ensure that virus is readily detected but at a level that reduces the risk of symptomatic illness and virus transmissibility.

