3.1.2 Study Design

This study will include 4 cohorts of 14 ZIKV and DENV-naïve female and male subjects, 18 - 40 years of age (total: up to 56 subjects). Within each cohort, 10 subjects will receive ZIKV and 4 subjects will receive a placebo on Study Day 0. Cohorts 1 and 2 (Dose = 10^2 PFU) will be enrolled first and will enroll only women. Cohorts 3 and 4 (Dose = 10^2 PFU) will enroll men.

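### The suitability criteria given to the DSMB in Section 7.6.3 omit the duration criterion that the Precis and Section 2.1 require

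*Combined protocol and SAP*

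**What the plan says.** The Precis and Section 2.1 define a suitable strain by three criteria joined by *and*: viremia by culture in at least 80% of inoculated subjects, a duration criterion, and a peak titer of 2–3 log10 PFU/mL. The duration criterion begins "Infectious virus is detected on more than 1 day for" and sets the threshold at 80% or more of the subjects with detectable viremia.

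Section 7.6.3 makes the DSMB responsible for the determination: "Determining if the criteria for a suitable CHIM strain has been met. These criteria are". Item a) is at least 80% "of inoculated subjects develop detectable viremia by virus culture". Item b) begins "The mean peak titer of ZIKV recovered is" and gives the same 2–3 log10 range. Item c) has the board review clinical findings, but "signs and symptoms will not be required for dose escalation". Duration does not appear.

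The titer criterion is also worded in two ways. The Precis has "The geometric mean peak titer of virus recovered by culture is". Section 2.1 has "The mean peak titer of infectious virus recovered from subjects is", and Section 7.6.3 likewise says only *mean*.

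Section 3.1.2.2 contains a related test. The second block of seven may be enrolled only if at least 4 subjects have infectious virus for at least 2 days (and other conditions hold).

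**The concern.** Choosing a suitable strain is the primary objective, so these criteria are the trial's main decision rule. The body charged with applying the rule has a shorter list than the objective, and that list is introduced as if complete. No section says which version governs. A strain with frequent viremia at the right titer, but with virus on a single day in too many subjects, would pass in Section 7.6.3 and fail in Section 2.1.

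Cohorts 3 and 4 and the final determination are still to come, and the DSMB sees unblinded summaries. A rule reconciled after those results are seen would be open to challenge.

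**Working it through.** **Inputs.** "Within each cohort, 10 subjects will receive ZIKV and 4 subjects will receive a placebo on Study Day 0" (Section 3.1.2). The first block has 5 ZIKV recipients (Section 3.1.2.1). The expansion rule needs at least 4 subjects with virus for at least 2 days (Section 3.1.2.2). The duration criterion needs at least 80% of viremic subjects, which is 8 of 10 if all are viremic. The documents give no true rate q of virus on more than one day among viremic subjects, so q is varied as an assumption.

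**The plan's own figures.** 10^1.67 = 46.8 PFU/mL (ZIKV-SJRP, Section 1.3.2.3) and 10^3.63 = 4,266 PFU/mL (ZIKV-Nicaragua, Section 1.3.2.4). Both reproduce.

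**Duration: how often the two lists could differ.** Assume all recipients are viremic. Let X1 and X2 be the numbers with virus on more than one day in the first and second blocks, each binomial(5, q). The cohort passes expansion and then fails the duration criterion if X1 ≥ 4 and X1 + X2 ≤ 7:

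P = P(X1 = 4)·P(X2 ≤ 3) + P(X1 = 5)·P(X2 ≤ 2).

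At q = 0.8: 0.4096 × 0.2627 + 0.3277 × 0.0579 = 0.1076 + 0.0190 = 0.127.

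| Assumed q | P(expansion duration test passed) | P(fails duration, given passed) | Joint chance |
|---|---|---|---|
| 0.5 | 0.188 | 0.760 | 0.14 |
| 0.6 | 0.337 | 0.583 | 0.20 |
| 0.7 | 0.528 | 0.374 | 0.20 |
| 0.8 | 0.737 | 0.172 | 0.13 |
| 0.9 | 0.919 | 0.035 | 0.03 |

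For example, 4 of 5 in the first block followed by 3 of 5 in the second passes expansion and ends at 7 of 10. These figures concern the duration test alone. The two lists give different answers only if the titer criterion is also met.

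**Reported data under both lists.**
- ZIKV-SJRP: all 10 recipients were viremic, and serum virus by culture lasted 4–6 days (Table 5), so duration is met in all. The mean peak of 1.67 log10 is below 2.0. Both lists say not suitable.
- ZIKV-Nicaragua (5 unblinded recipients): all 5 were viremic, and the mean peak of 3.63 log10 is above 3.0. Both lists say not suitable, whatever the duration result.

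**Type of mean.** If 1.67 is the mean of log10 peaks, the ten log values sum to 16.7. Section 1.3.2.3 puts eight peaks below 2 log10 and two between 2 and 3 log10. The arithmetic mean on the PFU scale is then bounded as follows.
- Lowest: two peaks at 100 and eight equal at 10^((16.7 − 4)/8) = 38.7. The mean is (200 + 309.4)/10 = 50.9 PFU/mL, or 1.71 log10.
- Highest, with an assumed floor of 0.5 log10 per subject: two at 1,000, four at 100, three at 3.16 and one at 10^1.2 = 15.8. The mean is 2,425/10 = 243 PFU/mL, or 2.38 log10.
- A lognormal with 20% of peaks above 2.0 log10: SD = 0.33/0.842 = 0.392, and 1.67 + (ln 10/2) × 0.392² = 1.85 log10.

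**The case against.** The strongest reply is that duration is already tested. Four of 5 recipients is 80%, and two days is more than one, so Section 3.1.2.2 applies the same threshold to the first block. The DSMB itself receives unblinded data to decide on expansion. This stands in part: it sharply lowers the exposure. It does not close the gap, because nothing repeats the test when the cohort reaches ten recipients.

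A reader might compute the chance of failing the duration criterion at ten recipients directly, as 1 − P(X ≥ 8), and get 95%, 83% and 62% at q = 0.5, 0.6 and 0.7. The arithmetic is correct, but it assumes every cohort reaches ten recipients. The expansion rule stops most cohorts with such low rates, so those figures overstate the risk.

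Low values of q also have no support in the data. Every ZIKV-SJRP recipient had at least four days of serum virus, and the Study Design text in the Precis expects kinetics in men not to differ significantly from those in women. Section 9.2 calls the study exploratory. These points limit the likely size of the problem; they do not reconcile the lists.

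On the mean, all three statements use log10 units, and Tables 2 and 3 attach symmetric errors to mean peak titers on that scale. That points to a mean of log10 values, which is the geometric mean. This objection largely stands.

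**Conclusion.** The contradiction is real. The DSMB's list lacks a criterion that the primary objective requires. The joint chance of passing expansion and then failing that criterion is about 13–20% at assumed rates of 50–80% and 3% at 90%, with all recipients viremic. The rates are assumptions, and the reported durations point to the favourable end.

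A reader might infer that the verdict on one of the two strains already depends on which section is used. The documents do not support that: through the duration criterion, neither reported result changes.

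A reader might also infer that ZIKV-SJRP passes or fails on titer according to the type of mean. That needs *mean* to be read as arithmetic on the PFU scale. On that reading the value could lie anywhere from about 1.71 to 2.38 log10, because individual titers are not given. A crossing of 2.0 is possible but not shown, and the lognormal matched to the reported spread gives 1.85, still below the limit. The wording of the mean is a minor clarification.

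**What to change.** Reconcile the Precis, Section 2.1 and Section 7.6.3. Add the duration criterion of Section 2.1 to the Section 7.6.3 list as a binding item, joined to the other two by *and*. Keep item c): replacing the whole list with the text of Section 2.1 would delete the DSMB's review of signs and symptoms.

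In Sections 2.1 and 7.6.3, use the Precis term, geometric mean, and state that it is the mean of log10 peak titers.

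The cost is one added line and a short wording change in two sections. No threshold, sample size or data collection changes. It should be done before the DSMB makes its determination for cohorts 3 and 4.

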8 DATA COLLECTION AND MONITORING

8.1 Source Documentation and Data Collection

Complete source documentation (laboratory test reports, hospital or medical records, progress notes, observations, etc.) is required for every study subject for the duration of the study. The subject's study record must record his/her participation in the clinical trial and, after unblinding, the randomization inoculation received (with doses and frequency) or other concomitant medications or interventions administered, as well as any adverse reactions experienced during the trial.

Data from source documentation for subjects enrolled in the study will be entered into the Clinical Research Information Management System of the NIAID (CRIMSON) Data System.

The data entry is to be completed on an ongoing basis during the study. Data entry into CRIMSON will be performed by authorized individuals and each individual entering data into CRIMSON will have a unique user ID and password. Corrections to the data system shall be tracked electronically (password protected) with time, date, individual making the correction, and what was changed.

Corrections to the source document must be made by striking through the incorrect entry with a single line (taking care not to obliterate or render the original entry illegible) and entering the correct information adjacent to the incorrect entry. Corrections must be initialed and dated by the person making the correction whenever possible. Source documentation should support the data collected in CRIMSON **and** must be signed and dated by the person recording and/or reviewing the data.

The investigator is responsible for the accuracy, completeness and timeliness of the data reported to the Sponsor in the CRIMSON Data System. All data entered into CRIMSON should be reviewed by the investigator/designee and signed as required with written or electronic signature, as appropriate. Data reported in CRIMSON should be consistent with source documents or the discrepancies should be explained. Source documentation will be made available for review or audit by the Sponsor or designee and any applicable Federal authorities.

8.2 Study Documentation

Study-related documentation will be completed as required by the IRBs, the Sponsor, and regulatory authorities. Continuing review documentation will be submitted by the investigator to the IRBs by the anniversary date of initial review as specified by each IRB. An annual report will be submitted by the Sponsor to the FDA according to regulations. These reports will provide a brief description of the progress of the investigation as outlined in the Code of Federal Regulations (CFR), Title 21, Part 312.33 (21 CFR 312.33), and will include any revisions of the protocol if not previously submitted.

The PI will maintain adequate records to account for the disposition of the investigational product, including dates of receipt and quantity, current inventory, and dispensation to subjects. If the study is terminated, suspended, or completed, all unused study product will be disposed of per sponsor's instructions.

8.3 Retention of Specimens

All specimens collected as part of this trial will be stored for future research as part of our approved biosample repository for vaccine research. These samples may be used to learn more about flavivirus infection and other diseases. These samples will not be sold or used to make commercial products. All samples stored in the repository will be labeled with the study ID numbers of the subjects that, by themselves, cannot identify study subjects, but are linkable to other research databases (e.g., from questionnaires, clinical assessments, logbooks, etc.) generated by the main study. A master log linking the study subject ID numbers to the names of the subjects will be maintained in a password protected database system with limited access to authorized research team members.

8.4 Retention of Records

The PI is responsible for retaining all essential documents listed in the International Conference on Harmonisation of Technical Requirements for Pharmaceuticals for Human Use (ICH) Good Clinical Practice (GCP) Guideline. Trial-related documents will be maintained by the investigator in a secure storage facility for a period of at least 2 years since the formal discontinuation of clinical development of the product. These records are also to be maintained in compliance with IRB, state, and federal medical records retention requirements, whichever is longest. The Sponsor is required to inform the investigator as to when such documents need no longer be retained. Storage of all trial-related documents will be such that confidentiality will be strictly maintained to the extent provided by federal, state, and local law.

It is the PI's responsibility to retain copies of source documents until receipt of written notification to the contrary from the OCRPRO of the NIAID. Study documents should not be destroyed without prior written agreement between OCRPRO/NIAID and the PI. Should the PI wish to assign the study records to another party and/or move to another location, the PI must provide written notification of such intent to OCRPRO/NIAID with the name of the person who will accept responsibility for the transferred records and/or their new location. NIAID must be notified in writing and written permission must be received by the site prior to destruction or relocation of research records.

8.5 Protocol Compliance

The PI will conduct the trial in compliance with the protocol agreed to by the Sponsor. The investigator will not implement any deviation from, or changes of, the protocol without agreement, prior review and documented approval by the Sponsor and the IRB that granted original approval for the study. The DSMB will be made aware of all protocol revisions (other than administrative) and will review any changes to the protocol that involve DSMB oversight or involve changes to the data and safety monitoring plan of the study.

However, the investigator may implement a deviation from, or change in, the protocol to eliminate an immediate hazard(s) to subjects without prior IRB or Sponsor approval or when the change(s) involves only logistical or administrative aspects of the trial (i.e., change of telephone number[s]). In the event of a medical emergency, the PI shall perform any medical procedures that are deemed medically appropriate.

As soon as possible, the implemented deviation or change, the reasons for it, and, if appropriate, the proposed protocol amendment(s) should be submitted to the Sponsor, IRB, DSMB, and to the regulatory authorities.

8.6 Clinical Investigator's Brochure

Investigators will receive the current versions of the Clinical Investigator's Brochures for the ZIKV strains used in this protocol, which comprehensively describes all the available preclinical experience with the ZIKVs. If relevant new information becomes available during the trial, the investigators will receive a revised brochure, or an amendment to the current version.

